5.3.8 Mean change of maximum daily pain score for RP attacks

For each RP attack the pain experienced during the RP attack is scored rating from 0 (No pain) to 10 (Worst imaginable pain).

For the baseline week and for week 4 the mean maximum daily pain score over the 7 most recent days before a visit (Day 1 and Day 28 (-2/+1)), will be derived by calculating the mean maximum daily pain score on the days with RP attack information in the 7 most recent days.

Mean change of maximum daily pain scores between week 4 and baseline is derived as the mean of individual differences of week 4 maximum daily pain minus baseline maximum daily pain.

5.4 Subgroup analysis

Subgroups are defined by “use of background vasodilatory treatment” stratification factors:

- Ca-blockers
- PDE-5 inhibitors
- No background vasodilatory treatment

Descriptive statistics of primary and key secondary endpoints will be created for these 3 subgroups.

6 PHARMACOKINETIC ENDPOINTS ANALYSIS

The pharmacokinetic endpoints analysis of GS-248 will be described later in an amended version of the SAP.

Statistical Analysis Plan	Version 2.0		Page 24 of 25
Sponsor	Gesyntha Pharma AB	Protocol No	GS-2001

7 PHARMACODYNAMIC ANALYSIS

7.1.1 Percentage change in PGE₂ level in whole blood ex vivo from baseline to week 4.

PGE₂ levels are measured in a subgroup at pre-selected sites. The endpoint is the percentage change from baseline at week 4.

No modelling will be done.

Descriptive statistics of the observed cases will be created for these parameters at baseline, week 4, change from baseline and percentage change from baseline at visit 4.

A by-treatment boxplot will be created for the percentage change from baseline at week 4.

7.1.2 Percentage change in levels of PGEM, PGIM and TXM (AA-metabolites) in urine from baseline to week 4.

Results for AA_metabolites will be corrected for urinary creatinine concentration in the following way:

Urinary creatinine is measured in mg/dL, this results in the following formula for the AA_metabolite in ng/mg:

AA_metabolite concentration in ng/mg=(100*AA-metabolite analyte concentration in ng/ml)/(Creatinine concentration in mg/dL).

The endpoint is the percentage change from baseline at week 4 of the AA_metabolite.

Descriptive statistics will be created for the observed cases of AA metabolites expressed in ng/mg) at baseline, week 4, change from baseline (in ng/mg) and for percentage change from baseline at week 4.

A by-treatment boxplot will be created for the percentage change from baseline at week 4.

7.1.3 Percentage change in levels of biomarkers in blood/plasma from baseline to week 4.

The following biomarkers for inflammation and endothelium dysfunction are predefined:

- hsCRP
- Endothelin-1
- sE-selectin
- xICAMI
- TNF
- IL-1b
- IL-4
- IL-6
- IL-10
- s-PECAMI CXCL-4

Statistical Analysis Plan	Version 2.0		Page 25 of 26
Sponsor	Gesyntha Pharma AB	Protocol No	GS-2001

- CD40L
- von Willebrand factor

The endpoint for these parameters is the percentage change from baseline at week 4.

Descriptive statistics of will be created for the observed cases of biomarkers at baseline, week 4, change from baseline and for percentage change from baseline at week 4.

A by-treatment boxplot will be created for the percentage change from baseline at week 4.

7.1.4 Expression of platelet surface markers.

The FACS (Fluorescence-activated cell sorting) at pre-selected sites was cancelled by the sponsor. Available FACS data gathered prior to the cancellation will be listed.

7.1.5 Change in microvascular volume from baseline to week 4 (D-OCT)

Microvascular volume (plexus depth, vessel diameter, vessel density microvascular volume) is measured in a subgroup at one pre-selected site.

No modelling will be done.

Descriptive statistics of the observed cases will be created for the microvascular volume at baseline, visit 4 and change from baseline at week 4.

8 SAFETY

The Safety Analysis Set (SAS) will be used for the analysis of safety data.

8.1 Adverse events

All AEs occurring during the course of the study will be coded using the latest MedDRA coding dictionary at the time of DBL. All AEs (serious and non-serious) reported from the first day of study treatment up until and including 7 days after the last dose of study treatment will be considered treatment emergent AEs (TEAEs).

Where dates are missing or partially missing, AEs will be assumed to be treatment-emergent, unless there is clear evidence (through comparison of partial dates) to suggest that the AE started prior to the first dose of study treatment or more than 7 days after the last dose of study treatment.

Verbatim terms will be coded by Ergomed and all relevant codes will be stored in the database. It is assumed that for each change in intensity, relationship or seriousness of an AE a new entry of the AE was recorded in the data capture database; hence such cases will be analysed like different phases of the same AE.

Subjects experiencing more than one AE within a given SOC category will be counted only once when calculating the number and percentage of subjects experiencing that SOC (e.g., a subject that experiences both nausea and vomiting will only be counted once in such calculations for the SOC gastrointestinal disorders). Similarly, subjects experiencing the same AE

Statistical Analysis Plan	Version 2.0		Page 26 of 27
Sponsor	Gesynta Pharma AB	Protocol No	GS-2001

multiple times throughout the course of the trial will be counted only once when calculating the number and percentage of subjects experiencing that PT (e.g., a subject that experiences mild nausea in both the first and fourth treatment cycle will only be counted once in such calculations for mild nausea). If a PT is reported at more than one severity level for a given subject, the greatest severity will be presented in the summary table.

If the same PT is reported multiple times for a given subject, but with varying study drug relationship assignment, the worst-case attribution will be presented in the summary table.

An AE is considered drug-related if the relationship to study drug is classified as either ‘Possible’ or ‘Probable’.

The following AE summaries will be provided:

- An AE overview table will be created displaying the number of TEAEs, number/percentage of subjects experiencing any TEAE, deaths, any SAE, any TEAEs causing discontinuation, any severe TEAE and any drug-related TEAE per treatment group.
- A summary of the number of events (TEAEs) by treatment group, SOC and PT
- A summary of the number and percentage of subjects reporting a TEAE by treatment group, SOC and PT
- A summary of the number of TEAEs by treatment group, intensity and PT
- A summary of the number and percentage of subjects reporting a TEAE by treatment group, intensity and PT
- A summary of the number and percentage of subjects reporting a TEAE by treatment group, relationship and PT
- A summary of the number of subjects reporting a TEAE with a frequency of $\geq 2\%$ by treatment group and PT
- A summary of the number and percentage of subjects reporting a non-serious adverse event occurring in greater than 5% of subjects by treatment group, SOC and PT

TEAE summaries will be ordered in terms of international order of SOC, and alphabetically for PT within SOC.

For the summary of TEAE with a frequency of $\geq 2\%$ TEAEs will be ordered by decreasing frequency.

For each subject and each AE, the worst intensity recorded will be attributed and used in the by-intensity summaries. Similarly, the worst relationship will be attributed and used in the by-relationship summaries.

All adverse events (i.e. TEAEs as well as non-treatment emergent events) will be listed in section 16.2 of the CSR. However, only TEAEs will be summarized in the tables.

AE listings will be presented by treatment group and will include: subject identifier, treatment, age, sex, race, AE (PT and verbatim term), study day of onset, duration, intensity, seriousness, action taken, relationship, outcome and concomitant medication given (including CM number).

Statistical Analysis Plan	Version 2.0		Page 27 of 28
Sponsor	Gesynta Pharma AB	Protocol No	GS-2001

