## 6.2 Safety Assessments

### 6.2.1 Adverse Events

#### 6.2.1.1 Definitions

Per ICH, an AE is defined as any untoward medical occurrence in a subject or clinical investigation subject administered a pharmaceutical product and which does not necessarily have a causal relationship with this treatment. An AE can therefore be any unfavourable or unintended sign (including an abnormal laboratory finding), symptom, or disease temporally associated with the use of a medicinal (investigational) product, whether or not related to the medicinal (investigational) product. The AE may be any of the following:

- A new illness
- An exacerbation of a sign or symptom of the underlying condition or of a concomitant illness
- Unrelated to participation in the clinical study or an effect of the study medication or comparator drug
- A combination of 1 or more of the above factors

No causal relationship with the study medication is implied by the use of the term adverse event.

Planned or elective surgical or invasive procedures for pre-existing conditions that have not worsened are not AEs. However, any complication that occurs during a planned or elective surgery is an AE. Conditions leading to unplanned surgical procedures may be AEs.

When an AE occurs after written consent has been obtained but before the first dose of IMP, the AE will be considered a non-treatment emergent AE. An AE that occurs from the time the subject receives his/her first dose of IMP until his/her last study visit will be considered a treatment-emergent AE regardless of the assessed relationship to the administration of the IMP.

For the recording of pregnancy and relevant laboratory data see [Section 6.2.1.2](#).

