**Causality of Adverse Event:**

The Investigator must assess the causal relationship between an AE and the IMP using the definitions below and record it the AE Log of the eCRF. An AE is considered causally related to the use of the IMP when the causality assessment is probable or possible.

Probable:	The event has a strong temporal relationship to the IMP or recurs on re-challenge, and another aetiology is unlikely or significantly less likely.
Possible:	The event has a suggestive temporal relationship to the IMP, and an alternative aetiology is equally or less likely.
Unlikely:	The event has no temporal relationship to the IMP or is due to underlying/concurrent illness or effect of another drug (that is, there is no causal relationship between the IMP and the event).

*6.2.1.2 Recording Adverse Events*

All SAEs will be collected from the signing of the informed consent form (ICF) until the follow-up visit at the time points specified in the Overall Schedule of Assessments (SoA) (see [APPENDIX 2](#)).

All AE will be collected from the signing of the ICF until the follow-up visit at the time points specified in the SoA.

**Period: Subject Enrolment to the First Administration of IMP:** Non-treatment emergent AEs will be recorded from the time when the subject is enrolled into the study (date of signature of the informed consent) until first administration of IMP.

**Period: First Administration of IMP to Subject's last study visit:** Thereafter all AEs are treatment-emergent AEs (TEAEs, see Definitions, [Section 6.2.1.1](#)) and will be recorded until the final follow-up visit has been performed.

**Period after last study visit:** Any SAE occurring after the subject's last study visit but considered by the investigator to be related to the IMP will be recorded.

If an AE (serious or not) started during the study but did not end before the final follow-up visit, the investigator should make a reasonable effort to establish the outcome and the end date. If this is not possible, the outcome recorded at the final follow-up visit will be assumed to be the final outcome.

If an event stops and later restarts, all the occurrences must be reported. AEs assessed as related to study medication by the investigator and all SAEs must be followed up until resolution.

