**APPENDIX 3: DETAILED SCHEDULE OF ASSESSMENTS – VISIT 2**

	≥30-0	Minutes (time window +/- 5 minutes, exact time recorded in eCRF)										
		0	30	60	90	120	150	170	175	180 (180-195)	200	
Arrival at site	X											
Morning urine sample collection (AA-metabolites, urine creatinine)	X											
Physical examination (minimum DU)	X											
Vital signs (BP, heart rate)	X											
ECG	X							X				
Nailfold capillaroscopy (if not performed at Visit 1)	(X)											
Pregnancy test (WOCBP) (urine dipstick)	X											
Drug Screen a	X											
Urinalysis (dipstick)	X											
Review of eDiary compliance	X											
Concomitant medication	X											
Inclusion/exclusion criteria	X											
Clin chem and haematology	X											
Biomarkers (blood) b	X											
Collect blood and urine for Biobank	X											
Randomisation	X											
Adverse Event	X c											
IMP administration		X d										
ASRAP questionnaire			X									
PK sampling sparse											X	
IMP dispensation												X
Assessments below will be conducted at pre-selected sites												
PGE2 levels in whole blood	X											
Platelet activation (FACS) e	X											
Microvascular volume (D-OCT)	X										X	

a. For presence of alcohol or prohibited substances, e.g. cocaine

b. hsCRP, Endothelin-1, sE-selectin, ICAM1, TNF, IL-1b, IL-4, IL-6, IL-10, s-PECAM1 CXCL-4, CD40L and von Willebrand factor

- c. AE collection reflecting the time from the previous visit as well as any AEs experienced during the day.
- d. IMP will be administered with food.
- e. Analysis of surface markers of platelet activation performed by FACS analysis at a local laboratory.

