**DETAILED SCHEDULE OF ASSESSMENTS COLD CHALLENGE/THERMOGRAPHY – VISIT 2**

The detailed schedule of assessment below describes the **additional** assessments at Visit 2 if the subject is enrolled to Cold Challenge.

	Session 1 										Session 2 				
	Minutes (time window +/- 5 minutes, exact time recorded in eCRF)														
	0 (0-15)	30	80	100	120 	0	30	60	90	120	150	170	175	180 (180-195)	200
Cold Challenge / Thermography															
Finger temperature															
Cold challenge with thermography every 15 seconds	X														
Thermography			X	X	X	X	X	X	X	X	X	X	X	X	

 Session 1 is conducted after randomization and prior to IMP administration.

 Session 2 starts at the same time as IMP administration, see DETAILED SCHEDULE OF ASSESSMENTS – VISIT 2.

 Estimated that skin temperature has returned to normal at 120 minutes, otherwise wait until it has returned to normal.

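### SAP 8.1 starts the treatment-emergent period at the first treatment day and by report, not at the first dose and by onset, so Day 1 pre-dose events are misclassified

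*SAP*

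**What the plan says.** SAP 8.1 gives the main rule: "All AEs (serious and non-serious) reported from the first day of study treatment" count as TEAEs, and the window closes 7 days after the last dose. The next paragraph covers missing or partial dates. It presumes an event treatment-emergent unless there is clear evidence "to suggest that the AE started prior to the first dose of study treatment" or that it began more than 7 days after the last dose. The first rule speaks of report and day, the second of start and dose.

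Protocol 6.2.1.1 works by occurrence and by dose throughout. For an event after consent "but before the first dose of IMP, the AE will be considered a non-treatment emergent AE". At the other boundary, "An AE that occurs from the time the subject receives his/her first dose of IMP until his/her last study visit will be considered" treatment-emergent. Protocol 6.2.1.2 repeats the split: "Non-treatment emergent AEs will be recorded from the time when the subject is enrolled into the study", and that period ends at the first administration of IMP.

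Two entries in protocol Appendix 3 show why the wording matters here. The AE assessment at Visit 2 sits in the pre-dose column, and its footnote reads "AE collection reflecting the time from the previous visit as well as any AEs experienced during the day". For the cold challenge subset, "Session 1 is conducted after randomization and prior to IMP administration".

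SAP 2.2, which lists changes from the protocol, names the FAS and PKAS definitions only. SAP 8.1 adds that AE tables summarise TEAEs only; other events are listed.

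**The concern.** Day 1 is both the first treatment day and a day with a substantial pre-dose period. Blood is drawn before dosing in all subjects. In the cold challenge subset, patients with Raynaud's phenomenon immerse their hands in cold water and are then observed, still before the first capsule. An AE in that period cannot be caused by GS-248, and the protocol says so by definition. The SAP nevertheless counts it.

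Basing the rule on report adds a second problem. AEs are collected mainly at visits, so the date of report can lie weeks after onset. A rule tied to it can move events into or out of the window for reasons unrelated to exposure.

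What is at stake is the AE summary in SAP 8.1 and 8.2. Events unrelated to drug would be added to the TEAE figures of both arms, which raises the rates quoted for GS-248 and pulls the ratio between arms towards 1. Two programmers could also reach different tables from the same data, because complete and partial dates follow different start points.

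**Working it through.** The plan states no figure for this point, so there is none to reproduce. The check sets the rules side by side and applies them to specific events.

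**Inputs**
- First treatment day: Day 1 = Visit 2 (protocol 3.1).
- Run-in: Visit 1 on Day -21 to -14 (protocol 7.1.1).
- Last dose: Visit 4, Day 28 (-2/+1) (protocol 3.1).
- Next scheduled AE collection: Visit 5, 2-3 weeks after the last dose (protocol 3.1, Appendix 2).
- Cold challenge subset: an estimated 50 subjects (protocol 8.10, SAP 1.5).
- Session 1: thermography to about 120 minutes, longer if skin temperature has not recovered (Appendix 3).

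**Step 1: classify five events**

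| Event | Protocol 6.2.1.1 | SAP 8.1 by report date | SAP 8.1 by onset date |
|---|---|---|---|
| A. Starts in run-in, first reported at Visit 2 | No | **Yes** | No |
| B. Starts on Day 1 before the dose | No | **Yes** | **Yes** |
| C. Starts on Day 1 after the dose | Yes | Yes | Yes |
| D. Starts 3 days after last dose, first reported at Visit 5 | Yes | **No** | Yes |
| E. Starts 10 days after last dose | Yes | **No** | **No** |

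Bold marks disagreement with the protocol. B is misclassified however *reported* is read. A and D go wrong only on the literal reading. E reflects a different end of window (last dose + 7 days against last study visit), which may be deliberate but is not declared in SAP 2.2.

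**Step 2: timing behind D.** The SAP window closes 7 days after the last dose. Visit 5 is 14 to 21 days after it. The gap is 14 - 7 = 7 to 21 - 7 = 14 days. Unless the subject contacts the site earlier, an event in the 7-day tail is first reported after the window has closed.

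**Step 3: can B be separated with the data named?** Protocol 6.2.1.3 names dates of onset and resolution. SAP 4.1.3 derives study day from dates, and the AE listing shows study day of onset. All Day 1 events carry study day 1, before or after dosing. The documents name no onset clock time for AEs; whether the eCRF holds one cannot be seen from them.

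**Step 4: direction of the effect.** Let *p* be the risk of a true post-dose AE and *b* the risk of a pre-dose event, equal in both arms and independent of *p*. The tabulated risk is q = 1 - (1 - p)(1 - b), so the risk difference is multiplied by (1 - b). The values below are assumptions, not document figures, and show direction only. With true risks of 40% and 20% (difference 20 points, ratio 2.0):
- b = 5%: 43% and 24%, difference 19 points, ratio 1.79.
- b = 10%: 46% and 28%, difference 18 points, ratio 1.64.
- b = 20%: 52% and 36%, difference 16 points, ratio 1.44.

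For event counts, adding the same expected number to each arm leaves the difference unchanged and shrinks only the ratio.

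**The case against.** The best defence is that the SAP means onset and has merely chosen a loose word. Its missing-date rule compares start dates, its AE listing carries study day of onset, and it foresees a category of non-treatment-emergent events that a literal reading would nearly empty. The 7-day tail also works properly only if onset governs. I accept this: the onset-based reading is the likely one.

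The second defence is that, with dates only, counting every Day 1 onset is a cautious convention, in line with the SAP's default of presuming treatment-emergence when timing is unclear. That is reasonable where the timing really is unknown. It does not justify counting an event known to have started before the dose, which is what the rule does.

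A reader might go further and infer that the run-in adds 14/35 = 40% to 21/35 = 60% to the TEAE window, taking 28 + 7 = 35 days as the base. The documents do not support that. The figure uses report date to bring in the run-in and onset date to keep the tail. Applying report date to scheduled collection throughout gives 14 + 28 = 42 to 21 + 28 = 49 days, or 20% to 40% more than 35. Turning either range into AE counts needs a constant AE rate, which the documents do not give, and both rest on a reading that is probably unintended.

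A reader might also infer that all by-arm safety tables are affected. They are not: vital signs, ECG and laboratory summaries (SAP 8.3 to 8.5) do not use the TEAE definition.

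**Conclusion.** The point holds as a definitional error with small expected impact. The main rule in SAP 8.1 conflicts with protocol 6.2.1.1 and 6.2.1.2 and with the SAP's next paragraph, and the change is not declared in SAP 2.2. On any reading it counts AEs that start on Day 1 before dosing. The exposure is part of one day: blood draws in all subjects and about two hours of cold challenge and observation in an estimated 50. On the literal reading it also misplaces run-in events and events in the 7-day tail.

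The misclassified events should fall about equally on both arms, because treatment is randomised and blinded and the events precede dosing. This rests on the pre-dose procedures and AE collection being the same in each arm, as planned. No percentage inflation can be given. Safety analysis is primarily descriptive (protocol 8.6), so no formal test depends on it. It is worth correcting because it is cheap and it fixes one reproducible start point for the AE tables.

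**What to change.** In SAP 8.1, define a TEAE as an AE with onset at or after the time of the first IMP dose. State that onset, not report date, also decides whether an event falls within the end of the window. Use the same definition in the missing-date paragraph.

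Add a rule for Day 1: use the recorded onset time, or a pre-dose/post-dose flag or query, and count the event as treatment-emergent if its timing remains unknown.

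In SAP 2.2, list any difference from the protocol definition that remains, including the end of the window if last dose + 7 days is kept instead of the last study visit.

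The cost is a sentence or two in the SAP and, if onset time is not captured, one field or query for Day 1 events, to be resolved before database lock and unblinding.

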#### Treatment Period

On Day 1 (Visit 2, Baseline Visit) subjects will be reviewed for eligibility and subsequently randomised and receive their first dose of IMP under medical supervision at the study site. Study assessments, including PK sampling and safety, will be performed throughout this visit. In total, this visit will last for approximately 4 or 6 hours depending on whether the subject is enrolled in the cold challenge assessment or not. Subjects will be permitted to leave the study clinic for short time

periods between assessments as feasible but will be asked to remain on site. At the end of the visit, subjects will be dispensed sufficient amount of medication to last until the next study visit, scheduled for 14 ( $\pm 2$ ) days later.

Subjects will continue to fill in their eDiary throughout the Treatment Period.

On Day 15 ( $\pm 2$  days) subjects will return to the study site for Visit 3. Safety assessments, PK sampling and safety monitoring will be performed (see Overall Schedule of Assessments, [APPENDIX 2](#)). Treatment compliance will be checked, used bottle of IMP collected, and sufficient IMP for the remainder of the Treatment Period will be distributed. The visit will last approximately 1,5 hours.

Visit 4, End of Treatment Visit, will occur on Day 28 ( $-2/+1$  days), which will be the day subjects take their final dose of IMP, to be administered at the study site.

This visit will last for up to 5 hours, and for subjects undergoing rich PK sampling, this visit will last for up to approximately 9 hours. Additional safety and monitoring assessments will be performed (see [Appendix 4](#)).

The eDiary will be checked, and all IMP will be collected.

An ASRAP questionnaire will be completed by subjects, along with a Global Impression of Change, which is also completed by physicians.

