### **Follow-Up Period**

The follow-up visit (Visit 5, Day 42-49) should occur 2-3 weeks after the last dose of IMP. Safety assessments will be performed (see Overall Schedule of Assessments, [APPENDIX 2](#)). Subjects will complete the final entry in their eDiary, and these will be collected. The visit will last approximately 1,5 hours.

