2.2 Deviations from the trial protocol with regard to statistical analyses

The following deviations from the protocol were identified as being important for the statistical analysis:

Definition of FAS population was changed to include all randomised and treated subjects. And the requirement to have eligible data at visit 4 was removed.

Original text in protocol v4.0: The Full Analysis Set (FAS) includes all subjects who were randomized, received at least one dose of IMP and have evaluable data on the primary endpoint at visit 4.

The revised definition in the SAP: The Full Analysis Set (FAS), consists of all subjects that were randomised and received at least one dose of IMP.

Definition of PK Analysis Set (PKAS) was changed to include GS-248 treated patients only:

Original text in protocol v4.0: The PK Analysis Set (PKAS) consists of all subjects who received at least one dose of IMP within 30 hours before a blood sample for GS-248 bioanalysis was taken.

The revised definition in the SAP: The PK Analysis Set (PKAS) consists of all subjects who received at least one dose of GS-248 within 30 hours before a blood sample for GS-248 bioanalysis was taken.

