9 QUALITY CONTROL

The SAP was prepared by the TS. Particularly the TS has checked the consistency of the described methods and outputs with the actual version of the study protocol. In addition, a sponsor representative has reviewed the SAP before final approval.

Log files of all SAS[®] programs used in the analysis will be checked for errors, warnings and suspicious notes by the statistical programmer. All findings will be either eliminated or commented upon. The final version of each program will be stored along with its log file in the electronic archive.

All programs will be validated by the program author or an independent statistical programmer depending on the requested validation level selected in the List of TLFs form (FRM/BS/001.02) for a particular program.

The agreement of the program outputs with the SAP, their consistency and plausibility will be checked by the TS. Moreover, the TS will review the outputs regarding completeness, readability and comprehensibility.

The described process is associated with the 'normal' level of program validation. Additional levels of quality control can be specified in the List of TLFs (see Appendix, 1) for individual outputs.

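### SAP 8.1 ends the treatment-emergent window 7 days after last dose; the protocol runs it to the last study visit, 2-3 weeks after last dose, and the change is not declared

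*SAP*

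**What the plan says.** **Protocol.** Section 6.2.1.1 says that an AE occurring "from the time the subject receives his/her first dose of IMP until his/her last study visit will be considered a treatment-emergent AE", whatever its assessed relationship to the IMP. Section 6.2.1.2 repeats this for the period after first administration: "Thereafter all AEs are treatment-emergent AEs", and these "will be recorded until the final follow-up visit has been performed". Visit 4 is on Day 28 (-2/+1), "which will be the day subjects take their final dose of IMP". Visit 5, on Day 42-49, "should occur 2-3 weeks after the last dose of IMP". Sections 4.5 and 7.1.5 give subjects who stop early the same 2-3 week interval.

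**SAP.** Section 8.1 takes as treatment-emergent the AEs "reported from the first day of study treatment up until and including 7 days after the last dose of study treatment". Its rule for missing or partial dates uses the same 7-day limit, so the figure is deliberate and not a slip. The section then confines the summary tables to TEAEs and leaves all other AEs to listings. Section 8.2 places the death and SAE tables under a lead sentence saying that TEAEs are included.

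**Declaration.** SAP 2.2 opens with "The following deviations from the protocol were identified as being important for the statistical analysis" and names two items, the FAS and PKAS definitions. SAP 9 states that "the TS has checked the consistency of the described methods and outputs with the actual version of the study protocol".

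**The concern.** The two documents define the same term differently, and the SAP's definition decides what is tabulated. An event that starts ten days after the last dose is treatment-emergent under the protocol, but under the SAP it appears only in a listing.

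Incidence of AEs and incidence of SAEs are listed in both documents as safety endpoints of the primary objective. By-arm incidences produced under the SAP would follow a different definition from the one in the protocol, and a reader of the report would find no statement of the change. Neither document gives a reason for 7 days.

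Two wording problems add to this:

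- SAP 8.1 uses *reported* in the definition and *started* in the missing-date rule. No visit is scheduled between Visit 4 and Visit 5. Read literally, an AE that begins on the third day after the last dose but is first reported at Visit 5 could fall outside the window. Onset is the likely intent, but the text does not say so.
- The death tables in SAP 8.2 are labelled TEAE. The SAE tables, the death and SAE items of the overview table, and the non-serious AE table are not. Restriction to TEAEs is the natural reading of those tables, but not the only one.

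**Working it through.** **Inputs**

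- Last dose, L: Day 26-29 (Visit 4, Day 28 -2/+1; Protocol 3.1).
- Last study visit, V: Day 42-49, and 14-21 days after L (Protocol 3.1 and 7.1.5).
- End of the protocol window: V (Protocol 6.2.1.1).
- End of the SAP window: L + 7 (SAP 8.1).
- Arm size: about 40 (Protocol 3.1).

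**The plan's own figure.** With the nominal last dose on Day 28, 28 + 14 = 42 and 28 + 21 = 49. This reproduces Day 42-49 for Visit 5.

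**Formulas**

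- Uncovered days = V - (L + 7).
- Share of post-dose follow-up = (V - L - 7) / (V - L).
- Share of the protocol's TEAE period = (V - L - 7) / V, because the period runs from Day 1 to Day V.

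**All combinations that meet both visit rules**

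| L | V | Combinations | Uncovered days | Share of TEAE period |
|---|---|---|---|---|
| 26 | 42-47 | 6 | 9-14 | 9/42 = 21.4% to 14/47 = 29.8% |
| 27 | 42-48 | 7 | 8-14 | 8/42 = 19.0% to 14/48 = 29.2% |
| 28 | 42-49 | 8 | 7-14 | 7/42 = 16.7% to 14/49 = 28.6% |
| 29 | 43-49 | 7 | 7-13 | 7/43 = 16.3% to 13/49 = 26.5% |

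There are 6 + 7 + 8 + 7 = 28 combinations. The uncovered span is 7-14 days throughout. Its share of post-dose follow-up runs from 7/14 = 50.0% to 14/21 = 66.7%.

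**Sensitivity to the visit rules.** If only the calendar days are applied and the 2-3 week rule is dropped, the span is 6 days (L = 29, V = 42; 6/42 = 14.3%) to 16 days (L = 26, V = 49; 16/49 = 32.7%).

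**Early withdrawal, with Visit 5 14-21 days after the last dose**

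- Last dose on Day 1: 7/15 = 46.7% to 14/22 = 63.6% of the TEAE period.
- Last dose on Day 15: 7/29 = 24.1% to 14/36 = 38.9%.

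**Effect on a table entry.** One subject in an arm of 40 is 1/40 = 2.5 percentage points. A subject percentage changes only when the subject with a late event has no earlier TEAE in the same category. SAP 8.1 also has a table with a threshold of at least 2% and one with a threshold above 5%. If these apply per arm, one subject is enough to enter the first (2.5%). In the second, one more subject moves a term from 2/40 = 5.0% (out) to 3/40 = 7.5% (in), provided that table is restricted to TEAEs.

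**The case against.** The strongest reply is that a 7-day window is not shown to be wrong in itself. The documents give no half-life for GS-248, so the window cannot be called too short on pharmacological grounds. Safety analysis is descriptive (Protocol 8.6), no test depends on it, and the same rule applies to both arms. AE listings are presented by treatment group with study day of onset, seriousness and relationship, so at about 40 subjects per arm a reader could count the late events by hand. The numerical effect may be nil. All of this stands, and it limits the severity. It does not remove the conflict: the protocol's definition was complete, the SAP shortened it, and a hand count from a listing is not the by-arm incidence named as an endpoint.

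A second reply concerns versions. SAP 2.2 compares itself with protocol v4.0, which is not the text supplied, and it claims to list only important deviations. The v4.0 definition of a TEAE cannot be seen here. However, the supplied protocol already carries the FAS and PKAS wording that SAP 2.2 calls revised, and it still runs TEAEs to the last visit. SAP 2.2 names no TEAE change against any version. A change to how a primary-objective safety endpoint is counted is hard to class as unimportant.

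A third reply is that the SAE tables may not be restricted at all. That is possible, and SAE incidence would then be unaffected. The wording of SAP 8.1 and 8.2 favours restriction, and the text should settle the matter.

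**Conclusion.** The inconsistency is real and should be fixed. For a subject whose visits meet both rules, the SAP leaves out one to two weeks that the protocol counts, which is at least half of the post-dose follow-up.

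These figures measure calendar time, not events. By-arm incidences may differ from those under the protocol's definition, but by how much cannot be derived. The ranges assume that Visit 5 is held within its window. Visits moved under the COVID-19 provisions, and subjects lost to follow-up with no Visit 5, fall outside the calculation. How many subjects would withdraw early is also not known.

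For AE incidence the conclusion rests on explicit text. For the death tables it rests on their TEAE label. For the SAE, overview and non-serious AE tables it rests on the natural reading. Laboratory, ECG and vital-sign summaries are not affected. Detailed listings of fatal and other serious events are still planned.

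**What to change.** - In SAP 8.1, define a TEAE as an AE with onset from first dose to the last study visit (Visit 5 or Early Termination), matching Protocol 6.2.1.1. Replace *reported* with *with onset*.
- Use the same end point in the missing-date rule.
- State in SAP 8.1 and 8.2 that the overview, SAE, death and non-serious AE tables use this window.
- State that the optional Safety Follow-up Visit in Protocol 6.2.4.1, which comes after the last study visit, does not extend the window.
- If the sponsor also wants a 7-day window, present it as an additional table, and declare it with its reason in SAP 2.2.

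The cost is SAP wording and one derivation flag. No new data are needed, because the protocol already collects AEs to the follow-up visit. AE counts may rise in either arm.
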